4. STUDY DESIGN

The IS Cohort will enroll 20 participants initially and up to 30 participants with T2D on basal insulin therapy. Patients who sign the informed consent and are deemed eligible following a general and endoscopic screening will be enrolled in the study.

The index procedure and periprocedural care is described in the main protocol.

The background glucose-lowering medications at baseline and during follow up for each cohort are shown in **Figure 1**.

Eligible participants will be on long-acting insulin with or without short- or rapid acting insulin (up to 60 IU/day and no more than 30% of short/rapid acting components) with or without up to four stable dose of non-insulin glucose lowering medications for at least 3 weeks at baseline.

Post procedure, non-insulin background medications will be resumed to the baseline dose and maintained during the follow-up phase. Insulin dose will be titrated based on fasting glucose levels and may be discontinued if the daily insulin dose is reduced to 10 IU or 0.1 IU/kg and fasting glucose level is at target.

Participants will receive lifestyle-modification counseling sessions at scheduled intervals to promote adherence to a diet and lifestyle suitable for individuals with diabetes. Counseling will be provided by a member of the research team (endocrinologist, dietitian, nurse, etc.) trained in the delivery of lifestyle counseling for diabetes.

Participants will undergo the same follow up schedule, study procedures and data collection as those described in the main study protocol.

[figure not shown]

Figure 1. Insulin Cohort Design

5. STUDY POPULATION

Eligibility criteria for IS Cohort is outlined below. The NIS Cohort eligibility criteria is defined in the main protocol and is included below for reference.

5.1. Inclusion Criteria

Participants are eligible to be included in the study only if all of the following criteria apply:

	NIS Cohort	IS Cohort
1.	18-70 years of age	
2.	Current diagnosis of T2D	
3.	History of T2D for less than or equal to 10 years	Treatment with insulin for \leq 10 years
4.	HbA1C of 7.5-11.0% (58-97 mmol/mol), inclusive	HbA1C of 7.0%-9.5%, inclusive
5.	BMI 24-40 kg/m ² , inclusive	
6.	On stable non-insulin glucose lowering medications (1-4 medications) for at least 12 weeks prior to baseline visit	On basal insulin with or without short/rapid-acting insulin (up to 60 IU/day, and the short/rapid acting components \leq 30% of total daily dose) for at least 3 weeks prior to baseline visit
7.	Weight stability (defined as a $<$ 5% change in body weight) for at least 12 weeks prior to the screening visit	On none or up to four non-insulin glucose lowering medications, stable for at least 3 weeks (except TZD stable for at least 8 weeks) prior to baseline visit.
8.	Agree not to donate blood during participation in the study	
9.	Able to comply with study requirements and understand and sign the Informed Consent Form	
10.	Women of childbearing potential must be using an acceptable method of contraception throughout the study	
11.	Willing and able to perform self-monitoring blood glucose and comply with study visits and study tasks as required per protocol	

5.2. Exclusion Criteria

Participants are excluded from the study if any of the following criteria apply:

	NIS Cohort	IS Cohort
1.	Diagnosed with type 1 diabetes	

2.	History of diabetic ketoacidosis or hyperosmolar nonketotic coma	
3.	Probable insulin production failure, defined as overnight fasting C-peptide serum <1 ng/mL (333 pmol/L).	Fasting serum C-peptide <0.6 ng/ml (200 pmol/L)
4.	Previous use of any types of insulin for >1 month (at any time, except for treatment of gestational diabetes) in last 2 years.	Current use of any medication (such as psychoactive drugs such as carbamazepine, phenobarbital, sympathomimetics, corticosteroids and sex hormones, etc.) that can interfere with glucose metabolism
5.	Current use of insulin	Current use of inhalation insulin, or insulin pump
6.	Hypoglycemia unawareness	
7.	History of ≥ 1 severe hypoglycemia (defined by needing for third-party assistance), unless a clear correctable precipitating factor can be identified, in past 6 months from the screening visit	
8.	Known autoimmune disease, as evidenced by a positive anti-glutamic acid decarboxylase (GAD) test, including but not limited to celiac disease, or pre-existing symptoms of systemic lupus erythematosus, scleroderma or other autoimmune connective tissue disorder. (Participants with adequately controlled primary hypothyroidism may be included).	
9.	Previous GI surgery that has changed GI anatomy or could limit treatment of the duodenum, such as Billroth 2, Roux-en-Y gastric bypass, gastric band or other similar procedures or conditions.	
10.	Known history of a structural or functional disorder of the upper GI tract that may impede passage of the device through the upper GI tract or increase risk of tissue damage during an endoscopic procedure, including esophagitis, stricture/stenosis, varices, diverticula, or other disorder of the esophagus, stomach and duodenum.	
11.	Active H. pylori infection (Participants with active H. pylori may continue with the screening process if they are treated with an appropriate antibiotic regimen)	
12.	History of, or gastrointestinal symptoms suggestive of gastroparesis	
13.	Acute gastrointestinal illness in the previous 7 days	
14.	Known history irritable bowel syndrome, radiation enteritis or other inflammatory bowel disease, such as Crohn's disease and Celiac disease	
15.	History of chronic or acute pancreatitis	
16.	Known active hepatitis or active liver disease other than NASH/NAFLD	
17.	Alcoholic liver disease, as indicated by ANI > 0 and history of alcoholism.	

18.	Current use of anticoagulation therapy (such as warfarin) that cannot be safely discontinued periprocedurally.	
19.	Current use of P2Y12 inhibitors (clopidogrel, prasugrel, ticagrelor) that cannot be discontinued for 5 days before the procedure.	
20.	Unable to discontinue non-steroidal anti-inflammatory drugs (NSAIDs) during treatment through 4 weeks following the procedure. Use of acetaminophen and low dose aspirin is allowed.	
21.	Use of systemic glucocorticoids (excluding topical or ophthalmic application or inhaled forms) for more than 10 consecutive days within 12 weeks prior to the baseline visit.	
22.	Use of drugs known to affect GI motility (e.g. Metoclopramide)	
23.	Use of weight loss medications such as Phentermine, Meridia, Xenical, or over-the-counter weight loss medications (prescription medication)	
24.	Persistent anemia, defined as hemoglobin <10 g/dL.	
25.	Known history of blood donation or transfusion within 3 months prior to the Screening Visit.	
26.	Known history of cardiac arrhythmia	
27.	Significant cardiovascular disease, including known history of valvular disease, or myocardial infarction, heart failure, transient ischemic attack, or stroke within 6 months prior to the Screening Visit.	
28.	Estimated glomerular filtration rate (eGFR) ≤ 30 ml/min/1.73m ² .	Estimated glomerular filtration rate (eGFR) ≤ 45 ml/min/1.73m ² .
29.	Known immunocompromised status, including but not limited to individuals who have undergone organ transplantation, chemotherapy, or radiotherapy within the past 12 months, who have clinically-significant leukopenia, who are positive for the human immunodeficiency virus (HIV) or whose immune status makes the participant a poor candidate for clinical trial participation in the opinion of the investigator.	
30.	With any implanted electronic devices that can't be turned off during the procedure, or duodenal or biliary stent.	
31.	Not a candidate for upper GI endoscopy or anesthesia.	
32.	Active illicit substance abuse or alcoholism (> 2 drinks/day regularly).	
33.	Active malignancy within the last 5 years (excluding non-melanoma skin cancers)	
34.	Women breast feeding	
35.	Participating in another ongoing clinical trial of an investigational drug or device.	

36.	Any other mental or physical condition which, in the opinion of the study investigator, makes the participant a poor candidate for clinical trial participation.	
37.	Critically ill or has a life expectancy <3 years	
Additional exclusion criteria to be confirmed during the screening process:		
38.	HbA1c < 7.5% (58 mmol/mol) or > 11% (97 mmol/mol) at baseline visit	HbA1C <7.0% or >9.5% at baseline visit
39.	Any severe hypoglycemic event since the screening visit	
40.	Glucose level <54 mg/dl (3.0 mmol/l) in more than 1% of time by CGM since the screening visit	
41.	Uncontrolled hyperglycemia with a glucose level >270 mg/dl (>15 mmol/L) after an overnight fast or >360 mg/dl (>20 mmol/l) in a randomly performed measurement that is confirmed by a second measurement (not on the same day) since screening visit	
42.	Mean of 3 separate blood pressure measurements >180 mmHg (systolic) or >100 mmHg (diastolic)	
43.	Women of child-bearing potential with a positive urine pregnancy test at baseline visit	
44.	Grade III or greater esophagitis on endoscopy	
45.	Abnormalities of the GI tract preventing endoscopic access to the duodenum	
46.	Anatomic abnormalities in the duodenum that would preclude the completion of the treatment procedure, including tortuous anatomy	
47.	Endoscopic observation of upper gastrointestinal abnormality such as ulcers, duodenal polyps in the area to be treated, varices, strictures, congenital or intestinal telangiectasia	
48.	Any other anatomical or endoscopic abnormalities/characteristics that, in the opinion of the investigator, would preclude safe use of the investigational device or procedure.	

6. STUDY INTERVENTIONS AND CONCOMITTENT MEDICATIONS

Study interventions and concomitant medication management are the same as described in the main protocol with the exception of the glucose lowering medications and rescue criteria as described below.

6.1. Glucose-Lowering Medications

6.1.1. Insulin Medications

IS Cohort enrolls participants treated with basal insulin with or without S/RA insulin. The total daily insulin dose must be less than or equal to 60 IU. If a participant is also on S/RA insulin, the S/RA insulin must be less than or equal to 30% of the total daily dose. The insulin regime must be stable ($\leq 10\%$ change in insulin dose) for at least 3 weeks prior to baseline visit.

6.1.1.1. Allowed basal insulin includes

- Insulin degludec U-100 or U-200, once daily
- Insulin Glargine U-100 or U-300, once daily
- Insulin Detemir U-100, once or twice daily
- Human insulin Neutral Protamine Hagedorn (NPH), once or twice daily

6.1.1.2. Allowed bonus insulin includes

- Insulin lispro
- Insulin aspart
- Insulin glulisine
- Regular insulin

6.1.1.3. Allowed pre-mixed insulin includes

- NovoMix® 30 (30% rapid, 70% intermediate Protaphane)
- Humalog® Mix 25 (25% rapid, 75% intermediate Humulin NPH)
- Ryzodeg 70:30 (70% long acting Degludec, 30% rapid Aspart)
- Mixtard® 30/70 (30% short, 70% intermediate Protaphane)
- Humulin® 30/70 (30% short, 70% intermediate Humulin NPH).

For the index procedure, participants will be instructed to fast overnight. A general recommendation is to administer 50% of their typical insulin dose at their usual time typically the preceding evening or the morning of the procedure day. However, the investigator should individualize insulin management for each subject particularly if S/RA is a component of their insulin regime.

- Following the procedure, participant's baseline insulin dose will be reduced to avoid hypoglycemia in the setting of a reduced caloric intake post procedure. Subsequently the insulin dose will be titrated to achieve a fasting glucose target of 5.0 – 7.2 mmol/L. Specifically, the following algorithm will be instituted.
- Continue insulin at 50% of the baseline dose on day 1 post procedure.
- Increase insulin dose by 2 units or 10% (as per recommendation of the treating investigator or provider) if fasting glucose is above the target of 7.2 mmol/L over 3 consecutive days.
- Alternatively, reduce insulin dose by 2 units or 10% (as per recommendation of the treating investigator or provider) for a single morning blood glucose or CGM reading less 5.0 mmol/>, or any episode of symptomatic hypoglycemia.
- If daily insulin dose is reduced to 10 units or 0.1 units/kg and fasting glucose is within the target range, insulin may be discontinued with close follow up of glycemia through CGM.
- If insulin is not completely withdrawn by 24 weeks, the background therapy may be intensified to further decrease or eliminate reliance on exogenous insulin. Intensification of background therapy may include addition of a GLP-1a, or an SGLT2i if the participant is already taking or has demonstrated an intolerance to GLP-1a. The insulin titration following intensification of background glycemic therapy should follow the same algorithm as described above.

The above algorithm is provided as a guideline. Investigator should apply clinical judgement to individualize therapy including insulin dosing and background glycemic medications.

Participants in the IS cohort should be instructed to use CGM to monitor his/her glucose levels throughout the duration of the study.

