3. OBJECTIVES AND ENDPOINTS

The primary objective of the IS Cohort is to assess the feasibility and preliminary safety of the Endogenex device for endoscopic duodenal mucosal regeneration in individuals with T2D on insulin therapy.

The study will also assess, as exploratory endpoints, treatment efficacy, evaluated by changes in or maintenance of glycemic control in the absence of exogenous insulin therapy. **Table 1** below outlines the study objectives and endpoints. NIS Cohort is described in the main study protocol but listed here for reference.

Table 1. Study Objectives and Endpoints

Objectives	Endpoints	
	NIS Cohort	IS Cohort
Primary		
• To assess the safety of the Endogenex device for DMR procedure	• Proportion of participants experiencing one or more device- or procedure-related serious adverse events at 3 months post procedure.	
Secondary		
• To assess the technical feasibility of the Endogenex device for DMR procedure	• Procedure success: defined as successful treatment of at least 6 cm of duodenum segment. • Procedure time: defined as the time between the Endogenex catheter insertion and the catheter removal.	
• To assess changes in glycemic control	• Change from baseline in glycemic parameters post index procedure, by visits 
○ HbA1c○ Fasting plasma glucose (FPG)○ Insulin-resistance by HOMA-IR○ Post prandial plasma glucose (PPG), Beta cell function, disposition index by mixed meal tolerance test (MMTT) • Change in glucose-lowering medication usage	• Proportion of treated participants with an HbA1c improvement of 0.3% or more at 24 weeks from baseline • Proportion of treated participants with an HbA1c improvement of 0.3% or more at 24 weeks from baseline and maintained at 48 weeks

		of insulin at 24 weeks and maintained at 48 weeks

 To assess liver enzymes and other metabolic changes 	
 Change in liver enzyme from baseline at 24 weeks 
 Alanine Aminotransferase (ALT) Aspartate Aminotransferase (AST) Change from baseline in blood pressure and lipid profile by visit Change in weight from baseline by visit 	

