11. STATISTICAL DESIGN AND ANALYSIS

Statistical analysis will be performed in accordance with the main protocol. The data on safety and procedural feasibility will be analyzed for each cohort and overall. The data on efficacy endpoints will be analyzed by treatment cohort.

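### In the insulin cohort, change in FPG (and to a lesser degree HbA1c) is confounded by treat-to-target insulin titration in participants still on insulin, and no stated analysis links it to insulin dose

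*Protocol*

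**What the plan says.** The efficacy aim of the IS cohort (Appendix 4, Section 3) is "evaluated by changes in or maintenance of glycemic control in the absence of exogenous insulin therapy". Table 1 of that section lists "Change from baseline in glycemic parameters post index procedure, by visits", including HbA1c and FPG, and separately lists change in glucose-lowering medication usage. It also has an insulin-related endpoint at 24 weeks, maintained at 48 weeks. The table's cells are broken in the text available to me: I read the glycemic row as covering both cohorts, and I cannot read the full definition of the insulin-related endpoint.

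Appendix 4, Section 6.1.1.3 sets the insulin algorithm:

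- Target: "Subsequently the insulin dose will be titrated to achieve a fasting glucose target of" 5.0 to 7.2 mmol/L.
- Start: "Continue insulin at 50% of the baseline dose on day 1 post procedure".
- Up: add 2 units or 10% "if fasting glucose is above the target of 7.2 mmol/L over 3 consecutive days".
- Down: reduce by 2 units or 10% after a single reading below 5.0 mmol/L or any symptomatic hypoglycemia.
- Stop: "If daily insulin dose is reduced to 10 units or 0.1 units/kg and fasting glucose is within the target range, insulin may be discontinued".

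The algorithm is called a guideline. The only dose ceiling is at entry (Section 5.1): "On basal insulin with or without short/rapid-acting insulin (up to 60 IU/day".

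On analysis, Appendix 4, Section 11 says "The data on efficacy endpoints will be analyzed by treatment cohort" and otherwise defers to the main protocol. Section 11.4.3 there gives means, standard deviations, medians, ranges, counts and percentages.

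**The concern.** IS participants enter inadequately controlled on their current insulin. If the device did nothing, the algorithm would still raise insulin until fasting glucose reached the target. FPG would fall and HbA1c would probably follow. The medication-usage endpoint is a separate summary, so it cannot show whether the participants whose HbA1c fell are those whose insulin rose.

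The non-insulin cohort is better placed. Its background medication is held stable to Week 24 (main protocol, Section 6.2.1), and its per-protocol set requires that stability (Section 11.3). IS insulin is halved and titrated by design, so that set offers no equivalent check. The SAP does not help: it describes 20 patients on non-insulin agents under a different document number.

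At stake is the reading of the cohort's efficacy results. Its question is control with less or no insulin, and a pooled mean change in FPG or HbA1c can look favourable through more insulin.

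**Working it through.** The plan gives no effect size, power or sample-size calculation for this cohort, so there is no figure to reproduce. Two checks follow.

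**1. How soon the dose can pass baseline.** Inputs from Section 6.1.1.3: start at 50%, at most one increase per 3 days, step of 2 units or 10%. This is the fastest path, with every 3-day window above target and each change made at once.

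- 10% steps: ln(2)/ln(1.1) = 7.3, so 8 steps × 3 days = 24 days.
- 2-unit steps: (half of baseline ÷ 2) × 3 days. Baseline 20 IU: 5 steps, 15 days. 40 IU: 10 steps, 30 days. 60 IU: 15 steps, 45 days.
- Time left to Week 24 (day 168): (168 − 45)/7 = 17.6 weeks to (168 − 15)/7 = 21.9 weeks.
- With no stated maximum, a 60 IU participant persistently above target on 2-unit steps would reach 30 + 2 × 28 = 86 IU by Week 12 and 30 + 2 × 56 = 142 IU by Week 24. This is an arithmetic bound, not a forecast. It shows only that the 60 IU entry limit does not restrain follow-up.

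**2. What FPG change can show while insulin is titrated.** The documents give no baseline FPG for this cohort. If it is 8 to 10 mmol/L (assumption), reaching 7.2 is a fall of 8 − 7.2 = 0.8 to 10 − 7.2 = 2.8 mmol/L, whatever caused it.

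An illustrative model makes the point. Assume baseline dose 40 IU, baseline FPG 10 mmol/L, a fall of 0.1 mmol/L per IU and a device effect E on FPG. Then FPG = 10 + 0.1 × (40 − dose) − E. Setting FPG = 7.2 gives dose = 68 − 10E.

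| Device effect E (mmol/L) | FPG change at Week 24 (mmol/L) | Insulin dose (IU) |
|---|---|---|
| 0 | −2.8 | 68 |
| 1 | −2.8 | 58 |
| 2 | −2.8 | 48 |
| 3 | −2.8 | 38 |

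The assumptions were varied over baseline FPG 9 to 11 mmol/L, 0.05 to 0.15 mmol/L per IU and both step rules. For any one set of assumptions, the Week 24 FPG change then differed across device effects by at most about 0.7 mmol/L, in no consistent direction. In this model the device effect appears in the insulin dose and hardly at all in FPG. The model assumes that the algorithm is followed exactly and that nobody stops insulin.

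**The case against.** A reader might infer that FPG and HbA1c in this cohort measure the algorithm rather than the device. The documents do not support that.

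- Once insulin is stopped, the rescue criteria of Appendix 4, Section 6.2 apply in place of titration to target. The cited thermal-ablation study of 16 patients had 69% off insulin at 6 months. At that rate about 14 of 20 (0.69 × 20 = 13.8) or 21 of 30 (20.7) would have values outside the titration. That study's title shows it combined the procedure with GLP-1 receptor agonism, so the rate may not carry over. Even if it did, about 6 of 20 or 9 of 30 titrated participants would enter the same mean.
- HbA1c also reflects post-prandial glucose, which a fasting target does not fix.
- The algorithm works both ways and is a guideline, so the dose need not exceed baseline.

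A reader might also infer that halving an entry dose of 20 IU or less delivers insulin withdrawal by itself. It does not: stopping also needs in-range fasting glucose, which someone uncontrolled on the full dose would not be expected to reach on half of it without another effect. Nor can the insulin-related endpoint be criticised when its definition is not fully readable. It may already join glycemia to insulin status.

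Finally, efficacy here is exploratory, in a single-arm study with lifestyle counseling, and medication change is already listed. That limits the weight of the point. It does not remove it, because a descriptive result must still be readable and the two summaries are not linked.

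**Conclusion.** The point holds for participants who remain on insulin: FPG change is confounded by titration to a fasting target, HbA1c change less so, and no stated analysis connects either to insulin dose or status. Followed as written, the plan could show glycemic improvement with no device effect.

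The 17.6 to 21.9 weeks rest on the algorithm's fastest path and baseline doses of 20 to 60 IU. The size of any FPG fall rests on an assumed baseline FPG. The conclusion also assumes that the glycemic row of Table 1 covers the IS cohort, which the by-cohort efficacy analysis supports. It does not reach the primary safety endpoint or the feasibility endpoints, and it is no criticism of the algorithm as clinical management.

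**What to change.** Leave the algorithm as it is and add the following to Appendix 4, Section 11 (the SAP supplied does not cover this cohort):

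- At Weeks 24 and 48, the proportion with HbA1c no higher than baseline and total daily insulin no higher than baseline, reported beside the existing insulin-related endpoint.
- HbA1c and FPG change shown together with each participant's insulin dose change and on/off-insulin status at that visit.
- A flag on values recorded after rescue therapy or after an added GLP-1a or SGLT2i, which Section 6.1.1.3 allows if insulin is not withdrawn by 24 weeks.
- A statement that FPG change will not be presented alone as efficacy.

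Any breakdown by post-procedure insulin status or by entry dose should be labelled descriptive. Insulin status is itself an outcome, and 20 to 30 participants split several ways leave small groups. The joint summary rules out higher insulin as the explanation. It does not separate the device from counseling or other influences in a single-arm study.

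The cost is a paragraph and a few tables. Medication usage is already documented at each visit (main protocol, Section 7.2 and Appendix 2); the sponsor should confirm that the eCRF captures total daily insulin dose. The headline glycemic change may look less favourable.
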